## 9 ANALYSIS PERIODS

### 9.1 Current Study Period

The **Current Study Period** starts from the first dose date of study drug in Study 116 to the last day in Study 116.

The **Treatment-Emergent Period for the Current Study Period** starts on or after the first dose date of study drug in Study 116 to 14 days (inclusive) after the last dose of study drug in Study 116 or up to the last day in Study 116, whichever occurs first.

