#### Treatment Cohort

**Continuous variables** will be summarized using descriptive summary statistics: number of subjects, mean, standard deviation (SD), standard error (SE), median, minimum value (Min), and maximum value (Max). Precisions of the summary for continuous variables are detailed in [Appendix B](#).

**Categorical variables** will be summarized using counts and percentages. Percentages will be presented to 1 decimal place.

**Baseline:** The baseline value is defined as the most recent non-missing measurement (scheduled or unscheduled) before intake of the first dose of study drug in Study 115B, except specified otherwise.

- For ECGs, the baseline will be defined as the average of the pretreatment measurements on the start of Study 115B.
- For LCI-related parameters, the values at each visit will be calculated from the technically acceptable replicates. The baseline of LCI will be the most recent non-

missing value calculated from the technically acceptable replicates before the initial administration of study drug in the Study 115B.

- For sweat chloride, the values at each visit will be based on the averaged measurements from left and right arms. The baseline is defined as the average of the values at screening and the pretreatment measurement on Day 1 of Study 115B. For assessments where there is only 1 pre-first dose sweat chloride measurement available, that measurement will be considered the baseline.

**Change (Absolute Change) from baseline** will be calculated as

$$\text{Post-baseline value} - \text{Baseline value.}$$

**Relative change from baseline** will be calculated and presented in percentage as

$$100 \times (\text{Post-baseline value} - \text{Baseline value}) / \text{Baseline value.}$$

**Unscheduled visits:** Unscheduled visit measurements will be included in the analysis as follows:

- In scheduled visit windows per specified visit windowing rules.
- In the derivation of baseline measurements.
- In individual subject data listings as appropriate.

**Visit windowing rules:** [Appendix C](#) defines the visit window mapping rules to derive the analysis visits for study 116.

Repeated observations within the same visits window:

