#### **10.5.2 Clinical Laboratory**

For the laboratory measurements, the raw values and change from parent study baseline of the continuous hematology and chemistry results will be summarized in SI units at each visit in the Current Study Period (including all measurements from Study 116) for the overall group based on the 116 Safety Set.

For hematology and chemistry, the number and percentage of subjects with abnormal low (<lower limit of normal [LLN]) value and with abnormal high (>ULN) value at each scheduled time point in the Current Study Period will be summarized for the overall group based on the 116 Safety Set.

The number and percentage of subjects meeting the defined threshold criteria during the Treatment-emergent Period of the Current Study Period will be provided based on the 116 Safety Set. The threshold criteria are provided in [Appendix F](#).

Results of urinalysis will be listed in individual subject data listings only. In addition, a listing containing individual subject hematology, chemistry, and coagulation values outside the reference ranges will be provided. This listing will include data from scheduled and unscheduled time points.

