## Appendix F: Criteria for Threshold Analysis

**Table 13-5 Threshold Analysis Criteria for Laboratory Tests**

Parameter	Categorical change	Comments
Clinical Chemistry		
ALT	$\leq 3xULN$ *(Not a categorical change) $>3x - \leq 5xULN$ $>5x - \leq 8xULN$ $>3xULN$ $>5xULN$ $>8xULN$	FDA DILI Guidance Jul 2009.
AST	$\leq 3xULN$ *( Not a categorical change) $>3x - \leq 5xULN$ $>5x - \leq 8xULN$ $>3xULN$ $>5xULN$ $>8xULN$	FDA DILI Guidance Jul 2009.
ALT or AST	ALT $>3xULN$ or AST $>3xULN$	Vertex LFT working group 2014
ALT or AST	ALT $>5xULN$ or AST $>5xULN$	
ALT or AST	ALT $>8xULN$ or AST $>8xULN$	
Alkaline Phosphatase	$>1.5xULN$	FDA DILI Guidance Jul 2009.
Total Bilirubin	$>1.5x - \leq 2xULN$ $>2xULN$	FDA DILI Guidance Jul 2009.
ALT and Total Bilirubin	ALT $>3xULN$ and TBILI $>2xULN$	FDA DILI Guidance Jul 2009. To be counted within a same treatment phase, whatever the interval between measurements.
AST and Total Bilirubin	AST $>3xULN$ and TBILI $>2xULN$	FDA DILI Guidance Jul 2009. To be counted within a same treatment phase, whatever the interval between measurements.
(ALT or AST) and Total Bilirubin	(ALT $>3xULN$ or AST $>3xULN$ ) and TBILI $>2xULN$	Vertex LFT working group 2014
CPK	$>3x - \leq 10xULN$ $>10xULN$	FDA criteria Feb 2005. Am J Cardiol April 2006.
Creatinine	$\geq 150 \mu\text{mol/L}$ (Adults) $\geq 30\%$ change from baseline $\geq 100\%$ change from baseline	Benichou C., 1994.
Blood Urea Nitrogen	$\geq 17 \text{ mmol/L}$	
Chloride	$<85 \text{ mmol/L}$ $>115 \text{ mmol/L}$	
Sodium	$\leq 129 \text{ mmol/L}$ $\geq 150 \text{ mmol/L}$	

Potassium	<3 mmol/L ≥5.5 mmol/L	FDA Feb 2005.
Glucose		
Hypoglycaemia	≤3.9 mmol/L and <LLN	ADA May 2005.
Hyperglycaemia	≥11.1 mmol/L (unfasted); ≥7 mmol/L (fasted)	ADA Jan 2008.
Albumin	≤25 g/L	
Hematology		
WBC	<3.0 Giga/L (Non-Black); <2.0 Giga/L (Black) ≥16.0 Giga/L	Increase in WBC: not relevant. To be interpreted only if no differential count available.
Lymphocytes	>4.0 Giga/L	
Neutrophils	<1.5 Giga/L (Non-Black); <1.0 Giga/L (Black)	International Consensus meeting on drug-induced blood cytopenias, 1991. FDA criteria.
Monocytes	>0.7 Giga/L	
Basophils	>0.1 Giga/L	
Eosinophils	>0.5 Giga/L or >ULN (if ULN ≥0.5 Giga/L)	Harrison- Principles of internal Medicine 17th Ed., 2008.

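### The creatinine flag in SAP Table 13-5 compares any single Study 116 value with one pre-115B value, without size adjustment or repeat, so it can count children who have no kidney effect

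*SAP*

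**What the plan says.** - **Criterion.** SAP Appendix F, Table 13-5, gives creatinine an absolute limit of 150 µmol/L, marked for adults, and two relative rules: "\geq 30\%$ change from baseline $\geq 100\%$ change from baseline". In this population only the relative rules apply.
- **Baseline.** SAP 10.1 takes the "most recent non-missing measurement (scheduled or unscheduled) before intake of the first dose of study drug in Study 115B". For creatinine that is one value.
- **Direction.** Relative change "will be calculated and presented in percentage as" 100 × (post-baseline − baseline)/baseline. It is signed, so a change of at least 30% reads as an increase, although Table 13-5 does not state a direction.
- **Counting.** SAP 10.5.2 reports "The number and percentage of subjects meeting the defined threshold criteria during the Treatment-emergent Period of the Current Study Period". Under SAP 9.1 that period "starts on or after the first dose date of study drug in Study 116 to 14 days (inclusive) after the last dose", or ends on the last study day if that is earlier. No repeat value, ULN condition, or age or size adjustment is attached to the creatinine rows.
- **Schedule.** SAP Appendix A, Table 13-1, puts serum chemistry at Day 1 (predose), Day 15, Weeks 12, 24, 36, 48, 72 and 96, and at the ETT and Safety Follow-up Visits.

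**The concern.** The rule takes the worst of at least seven later values against one early one. Two things can push that ratio past 1.30 with no change in kidney function. One is within-child variation, biological and analytical together, which enters both the baseline and each later value. The other is any upward drift of creatinine as a small child grows, over an interval of more than two years.

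Elsewhere the SAP does allow for growth. Blood pressure is judged by percentiles adjusted for sex, age and stature (SAP 10.5.4), and weight, stature and BMI are analysed as age z-scores. Creatinine is not adjusted.

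Laboratory change is part of the primary endpoint, and the study has no control arm. A count in the ≥30% row therefore has no comparator to show how much of it is background. If creatinine drifts up, the background rate also rises with follow-up, which in a long-term safety study could be read as a cumulative effect.

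**Working it through.** The documents state no expected flag rate, so there is no figure of theirs to reproduce. The check asks how often the rule fires when the drug has no kidney effect.

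**Inputs from the documents**
- Study 115B treatment lasts 24 weeks (protocol 9.3.1), followed by a planned 2-week washout (SAP 9.2). Day 1 of Study 116 is then about week 26 after baseline, or later if there is a rollover gap.
- Day 15 falls at 24 + 2 + 2 = 28 weeks and Week 96 at 24 + 2 + 96 = 122 weeks.
- The seven scheduled post-dose values fall at weeks 28, 38, 50, 62, 74, 98 and 122. At 52.18 weeks per year, that is t = 0.54 to 2.34 years.

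**Assumed inputs (not in the documents)**
- Total within-child CV, c: 5% to 15%.
- Drift, g: 0% to 8% per year.
- Errors are log-normal and independent on every value, and follow-up is complete to Week 96.

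**Per-visit probability**

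P(t) = 1 − Φ{[ln 1.30 − t·ln(1+g)] / (s√2)}, with s = √ln(1+c²).

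For c = 10%, s = 0.0998, s√2 = 0.1411 and ln 1.30 = 0.2624.
- No drift: 0.2624/0.1411 = 1.86, so P = 3.1% at every visit.
- 5% per year, Day 15: (0.2624 − 0.0262)/0.1411 = 1.67, so P = 4.7%.
- 5% per year, Week 96: (0.2624 − 0.1141)/0.1411 = 1.05, so P = 14.7%.

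**At least one of the seven values ≥30% above baseline** (simulation, 400,000 children per cell; all visits share the one baseline)

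| Drift per year | CV 5% | CV 8% | CV 10% | CV 12% | CV 15% |
|---|---|---|---|---|---|
| 0% | 0.1% | 5.2% | 13.9% | 23.7% | 36.1% |
| 3% | 0.7% | 11.7% | 23.0% | 33.2% | 45.0% |
| 5% | 2.8% | 19.2% | 31.2% | 40.8% | 51.3% |
| 8% | 15.7% | 36.0% | 45.8% | 53.1% | 60.9% |

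**Further results from the same model**
- Growth with no noise reaches +30% by week 122 only if g ≥ 1.30^(52.18/122) − 1 = 11.9% per year, above every drift in the table.
- The ≥100% row is met by at most 1.8% in these cells.
- Counting changes in either direction raises the rate somewhat: 13.9% becomes 17.0% at CV 10% with no drift, and 53.1% becomes 55.6% at CV 12% with 8% per year.
- If follow-up ended at Week 48, the cell for CV 10% and 5% per year would fall from 31% to 21%.

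**The case against.** The strongest reply is that the size of the problem is not in the documents. That stands. The rate depends wholly on a CV and a drift that must be assumed, and with a CV of 5% and drift up to 5% per year it is negligible. A reader might infer from the middle of the table that some definite share of children, for example 14% to 53%, will be flagged. The documents do not support any such figure.

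A reader might also infer that the rule simply flags normal growth. The numbers do not show that either. The 14% cell has no growth in it, and no drift considered here crosses the threshold without noise. Much of the count comes from variation around a single baseline; drift adds to it and makes it rise with time.

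A third inference, that a false count could not be told apart from a renal signal, goes too far. The SAP also plans chemistry values and changes at each visit, counts above ULN at each visit, a listing of out-of-range values, a blood urea nitrogen threshold and urinalysis listings. The ≥100% row is almost immune. Table 13-5 speaks of categorical change and does not call the flag renal. These outputs help interpretation, but none of them removes a false flag from the ≥30% row.

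Finally, the percentages should not be turned into a number of children using the expected enrolment of 50. Study 116 includes an untreated Observational Cohort, and SAP 10.2.1 provides for children leaving treatment before Week 96 when commercial drug becomes available.

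**Conclusion.** The structural point holds on the text. One Study 116 value is compared with one value taken about 28 to 122 weeks earlier, in children who entered 115B at 2 through 5 years, with neither size adjustment nor a repeat. Flags can therefore arise with no kidney effect, and more often with longer follow-up if creatinine drifts up.

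The size is conditional: about 0.1% to 61% over CV 5% to 15% and drift 0% to 8% per year, assuming independent errors and complete follow-up to Week 96. The consequence is limited to reading one row of a descriptive, uncontrolled safety table. No treatment rule in the documents uses this threshold. Priority is low to moderate; the case for acting is that the change is cheap.

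**What to change.** Keep the existing creatinine rows in Table 13-5 and add:

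1. The ≥30% and ≥100% rules applied to creatinine divided by same-visit stature, relative to the same ratio at baseline. At best this removes the drift: at CV 10% and 5% per year, 31% would fall to about 14%. It does nothing about noise.
2. A row for ≥30% at two consecutive chemistry assessments. In the same model and cell, 31% falls to about 8% to 9% (8.4% in a check run of 400,000 children).

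Print the planned counts above ULN beside these rows. Do not make a value above ULN a condition of the flag: a child whose creatinine rises a great deal from a low baseline but stays within range would then be missed.

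**Cost.** SAP wording, one derived variable and a few table rows. Stature is scheduled at every chemistry visit and is a 115B baseline characteristic (SAP 10.2.2), so no new data are needed.

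**Downsides.** The added rows are not directly comparable with the standard table. A transient rise at one visit never reaches the consecutive row, and among the rows using creatinine itself it appears only in the existing one. A first rise at Week 96 can be confirmed only if a later chemistry value exists, so the SAP should say whether follow-up and unscheduled values count as the second assessment.

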**Table 13-6 Threshold Analysis Criteria for ECGs**

Parameter	Categorical change	Comments
HR	$\leq 50$ bpm and decrease from baseline $\geq 20$ bpm $\geq 120$ bpm and increase from baseline $\geq 20$ bpm $< 40$ bpm $< 50$ bpm $> 90$ bpm	
PR	$\geq 220$ ms and increase from baseline $\geq 20$ ms	
QRS	$\geq 120$ ms	
QTc	Absolute values (ms)	To be applied to any kind of QT correction formula.
Borderline	Borderline: 431-450 ms (Male); 451-470 ms (Female)	
Prolonged*	Prolonged: $> 450$ ms (Male); $> 470$ ms (Female)	
Additional	$\geq 500$ ms  Increase from baseline Borderline: Increase from baseline 30-60 ms Prolonged: Increase from baseline $> 60$ ms	

Note: Based on CPMP 1997 guideline.

**Table 13-7 Threshold Analysis Criteria for Vital Signs**

Parameter	Categorical change	Comments
Pulse Rate	$\leq 50$ bpm and decrease from baseline $\geq 20$ bpm $\geq 120$ bpm and increase from baseline $\geq 20$ bpm	To be applied for all positions (including missing) except STANDING.
Weight	$\geq 5\%$ increase from baseline $\geq 5\%$ decrease from baseline	FDA criteria Feb 2007.

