#### 8.1 Inclusion Criteria

1. Subject's legally appointed and authorized representative (e.g., parent or legal guardian) will sign and date an informed consent form (ICF) and the subject will sign and date an assent form (if applicable).

- 2. Subjects entering the **Treatment Cohort** must meet the following criteria:
  - Completed 24 weeks of LUM/IVA treatment and the Safety Follow-up Visit in Study 115B
    - Subjects who had study drug interruptions are eligible if they completed study visits up to the Safety Follow-up Visit of Study 115B. Subjects who are not taking LUM/IVA at the end of the Study 115B Treatment Period (i.e., Week 24), including subjects who have LUM/IVA treatment temporarily interrupted as of Day 1 in Study 116, must receive Vertex approval for enrollment in the Treatment Cohort.

Subjects entering the **Observational Cohort** must meet 1 of the following criteria:

- Completed 24 weeks of LUM/IVA treatment and the Safety Follow-up Visit in Study 115B, but do not want to enroll in the Treatment Cohort.
- Received at least 4 weeks of LUM/IVA treatment and completed visits up to Week 24 and the Safety Follow-up Visit, if required, of Study 115B but are not taking LUM/IVA at the end of the Study 115B Treatment Period (i.e., Week 24) because of a drug interruption and either did not receive Vertex approval to enroll in the Treatment Cohort or do not want to enroll in the Treatment Cohort.
- Permanently discontinued LUM/IVA in Study 115B after receiving at least 4 weeks of treatment and remained in the study from the time of treatment discontinuation through the Week 24 Visit and Safety Follow-up Visit, if required.
- 3. Willing to remain on a stable CF medication regimen through the Safety Follow-up Visit (Treatment Cohort only).
- 4. As deemed by the investigator, the subject's legally appointed and authorized representative (e.g., parent or legal guardian) must be able to understand protocol requirements, restrictions, and instructions. The subject's legally appointed and authorized representative should be able to ensure that the subject will comply with, and is likely to complete, the study as planned.

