### 9.2 Cumulative Study Period

The **Cumulative Study Period** starts from the first dose date of study drug in Study 115B to the last day in Study 116, regardless of

- 1) the planned 2-week Washout Period in Study 115B; and/or
- 2) the rollover gap between Study 115B and Study 116 (if any).

For subjects not enrolled in Study 116, the Cumulative Study Period will start from the first dose date of study drug in Study 115B to the last day in Study 115B.

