#### 10.5.4 Vital Signs

For the vital signs measurements, the raw values and change from parent study baseline values will be summarized at each scheduled time point of the Current Study Period (including all measurements from Study 116) based on the 116 Safety Set: systolic and diastolic blood pressure (mm Hg), body temperature (°C), pulse rate (beats per minute), respiratory rate (breaths per minute), as well as weight, stature, and BMI.

The number and percentage of subjects meeting the defined threshold criteria during the Treatment-emergent Period of the Current Study Period will be summarized based on 116 Safety Set. The threshold criteria are provided in [Appendix F](#).

Potentially abnormal SBP and DBP by their percentiles adjusted for sex, age and stature will be provided, including

- Number and percentage of subjects with categories:  $\geq 90\%$ - $<95\%$ ,  $\geq 95\%$ - $<99\%$  + 5 mmHg and  $\geq 99\%$  + 5 mmHg during the treatment-emergent period of the Current Study Period
- Number and percentage of subjects with SBP and DBP percentiles  $\geq 95\%$  once and twice during the treatment-emergent period of the Current Study Period
- Number and percentage of subjects with SBP and DBP percentiles  $\geq 95\%$  at each visit in the Current Study Period

The stature adjustment will be based on stature-for-age z-scores and their corresponding percentiles using the standard normal distribution ([Appendix H](#)). The stature percentiles will be further mapped per the following rules:

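### The weight-decrease count in SAP Table 13-7 uses the fixed pre-115B weight, so growth makes it increasingly insensitive to recent loss, and the visible SAP has no growth-adjusted subject count for weight

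*SAP*

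**What the plan says.** - **Criterion.** SAP Appendix F, Table 13-7 lists for weight "\geq 5\%$ increase from baseline $\geq 5\%$ decrease from baseline", with no adjustment for age or growth.
- **Baseline.** SAP 10.1 defines it as the "most recent non-missing measurement (scheduled or unscheduled) before intake of the first dose of study drug in Study 115B". The listed exceptions are ECG, LCI and sweat chloride. Weight is not among them.
- **What is counted, and when.** SAP 10.5.4 includes weight with the vital signs ("as well as weight, stature, and BMI") and tabulates the number and percentage of subjects "meeting the defined threshold criteria during the Treatment-emergent Period of the Current Study Period".
- **Window.** Under SAP 9.1 this period runs from the first Study 116 dose to "14 days (inclusive) after the last dose of study drug in Study 116" or the last day in Study 116, whichever is earlier.
- **Time before the window.** Protocol 8.1 requires of Treatment Cohort subjects "Completed 24 weeks of LUM/IVA treatment and the Safety Follow-up Visit in Study 115B". SAP 9.2 adds a planned 2-week washout and "the rollover gap between Study 115B and Study 116 (if any").
- **Growth-adjusted analysis.** Under SAP 10.3.2.3 the weight-for-age z-score is handled like the BMI z-score: raw value and change from the 115B baseline by visit, with a 95% CI and a plot of means. The general descriptive statistics in SAP 10.1 are "number of subjects, mean, standard deviation (SD), standard error (SE), median, minimum value (Min), and maximum value (Max").

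**The concern.** A fixed reference weight works in adults whose weight is stable. Protocol 9.3.1 describes the parent-study subjects as aged 2 through 5 years. Such a child must lose all the weight gained since the 115B baseline, and then a further 5% of baseline, before the decrease row registers anything. The increase row has the opposite problem: ordinary growth fills it.

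Safety is the primary objective of Study 116. A decrease count at or near zero could be read as reassurance that children did not lose weight, when the rule could hardly have shown otherwise late in the study. The same documents use growth-aware rules elsewhere. SAP 10.5.4 counts subjects by blood-pressure percentiles adjusted for sex, age and stature. Protocol 11.4.4.1, List B, measures weight loss against the highest value, or by a percentile crossing, over the past 6 months, but only as a sign of pulmonary exacerbation.

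**Working it through.** **Timing.** The plan gives no figure for the sensitivity of this row, but its visit days can be reproduced. Week 96 is day 96 × 7 + 1 = 673 and follow-up is day 98 × 7 + 1 = 687, as in SAP Appendix C. Weeks from the 115B baseline, with no rollover gap:

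- Study 116 Day 1: 24 + 2 = 26
- Day 15, the first scheduled weight after dosing: 26 + 2 = 28
- Week 48: 26 + 48 = 74
- Week 96: 26 + 96 = 122
- Latest end of the window: 122 + 2 = 124

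**Loss needed.** Let W0 be baseline weight, g the yearly gain and t the weeks since baseline. With linear growth, W(t) = W0 + g × t/52.18. The decrease row needs a weight of at most 0.95 × W0, so the loss needed from current weight is 1 − 0.95 × W0/W(t). This equals 5% when g = 0. For any g > 0 it exceeds 5% and rises with t, so the direction needs no assumed rate.

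**Size.** W0 and g are assumptions; the documents give neither. For 14 kg and 2 kg/yr the trigger weight is 0.95 × 14 = 13.3 kg. At Week 48, W = 14 + 2 × 74/52.18 = 16.84 kg and the loss needed is 1 − 13.3/16.84 = 21.0%. At Week 96, W = 18.68 kg and the loss needed is 28.8%.

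| Assumed W0, g | Day 1 (t = 26) | Week 48 (t = 74) | Week 96 (t = 122) |
|---|---|---|---|
| 20 kg, 0.5 kg/yr | 6.2% | 8.3% | 10.2% |
| 14 kg, 1 kg/yr | 8.3% | 13.7% | 18.6% |
| 14 kg, 2 kg/yr | 11.3% | 21.0% | 28.8% |
| 14 kg, 3 kg/yr | 14.2% | 27.1% | 36.7% |
| 10 kg, 3 kg/yr | 17.4% | 33.4% | 44.2% |

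The Day 1 weight is taken before dosing, so that column only marks where the window opens.

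**Increase row.** Weeks to +5% = 0.05 × W0/g × 52.18. This is 18.3 weeks for 14 kg at 2 kg/yr, before Study 116 starts. It is 8.7 weeks for 10 kg at 3 kg/yr, and 104.4 weeks for 20 kg at 0.5 kg/yr (Study 116 Week 78). A 14 kg child stays out of the row through Week 96 only if gaining less than 0.05 × 14 × 52.18/122 = 0.30 kg/yr.

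**Simulation of the present rule against a 6-month look-back.** There were 200,000 children per case, weighed at weeks 0, 24, 26, 28, 38, 50, 62, 74, 86, 98, 110 and 122 (the week 24 weight in 115B is assumed). Weighing error was normal and proportional to weight, with SD 1% or 2% (assumed). Flags were counted at visits after Study 116 Day 1. The loss columns add a single 10% loss at Week 48. Each cell shows SD 1% / SD 2%.

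| Case | 10% loss flagged, present | 10% loss flagged, 6-month | No loss but flagged, present | No loss but flagged, 6-month |
|---|---|---|---|---|
| 14 kg, 2 kg/yr | 0% / 0% | 97% / 87% | 0% / 0% | 0% / 6% |
| 10 kg, 3 kg/yr | 0% / 0% | 62% / 58% | 0% / 0% | 0% / 2% |
| 20 kg, 1 kg/yr | 15% / 31% | 100% / 98% | 0% / 0.4% | 0% / 19% |
| 20 kg, 0.5 kg/yr | 91% / 75% | 100% / 99% | 0% / 2.3% | ≤0.1% / 29% |

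The flagged proportions include noise flags at other visits. Counting Week 48 alone lowers them by about one percentage point at most.

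**The case against.** **Weight is already analysed with growth taken into account.** Weight-for-age z-score is a named secondary endpoint, summarised by visit with minimum and maximum. Vital signs are listed by subject, and weight loss that the investigator judges clinically significant becomes an adverse event and is counted by preferred term. This stands, and it is why the point is minor. It does not close the gap. A mean and a minimum do not say how many children declined, listings must be read by hand, and adverse events depend on judgement.

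**The row does what it says.** It counts net loss since before treatment, and a child 5% below that weight a year or more later is an extreme case. This also stands. The fault is insensitivity to recent loss and the risk of misreading a low count, not a wrong calculation.

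**Stronger readings that the documents do not support.**
- A reader might infer that no growth-adjusted count exists anywhere. The SAP contents list shows redacted entries, so one can say only that the visible text has none.
- A reader might infer that a child with a real loss is moved into the increase row. The rows are not exclusive. A child of 16.84 kg who loses 10% weighs 15.15 kg, still 8.2% above a 14 kg baseline, but was in the increase row before the loss and would be there without it.
- A reader might infer that every child is followed to week 124. The window closes at the earlier of 14 days after the last dose and the last study day, and some subjects need no Safety Follow-up Visit.

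**Conclusion.** The point holds as a minor one. The fixed pre-115B baseline, the restriction to the Study 116 treatment-emergent period and the age of the children all come from the documents. Together they make the decrease row insensitive to recent loss in any child who grows, increasingly so over time. The increase row mainly reflects growth, although a child who never enters it is gaining poorly.

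Confidence is high for the direction. The size rests on assumed starting weights and linear growth: about 21% at Week 48 and 29% at Week 96 in the central case, with 8-33% and 10-44% across the range. A rollover gap would raise these figures. The analysis is descriptive, weight data are not lost, and no trial conclusion rests on this row alone.

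**What to change.** 1. Keep both weight rows in Table 13-7. Add a footnote that they are not growth-adjusted, that the increase row mainly reflects growth, and that a low decrease count is not evidence of no weight loss.
2. Add at least one growth-aware subject count. The preferred one is the number and percentage of subjects whose weight-for-age z-score falls from the 115B baseline by a cut-off that the sponsor fixes before database lock. It also picks up a child who stops gaining without losing weight.
3. As an alternative or an addition, count subjects with a decrease of at least 5% from their highest on-study weight (115B or 116) in the past 6 months, the look-back in protocol List B.

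**Cost.** One or two descriptive rows beyond the standard table, and a footnote. Weights are already collected at each clinic visit and z-scores are already derived, so no new data and no repeat weighing are needed. The 6-month row brings extra flags from weighing noise. In simulated children with no loss these are at most 0.1% at SD 1% but 2-29% at SD 2%, against 0 to about 2% for the present rule. At the worst figure, 0.29 × 50 is about 15 of the 50 expected subjects. That is the reason to add this row rather than replace the present one, and to prefer the z-score count.
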